This is an interventional study. Therefore, the safety monitoring will be conducted by an Independent Safety Monitor, [name], MD, PHD, Pulmonologist at MGH. Monitoring: Subjects will be monitored for any adverse health effects during the study by the PI and staff pulmonologists ([name] or [name]). A physician investigator will perform a physical exam prior to, and after the study and will also assess the subjects at times during the study as the subject's symptoms and vital signs warrant. If the subject develops severe coughing, has a respiratory rate > 35/min for > 5 min, SpO2 < 88% for 5 min and not corrected by administering extra O2 or if SpO2 < 80% at any time, a HR sustained < 50/min or > 140/min, or BP falls below 90/60 or rises above 160/90 with no history of hypertension at baseline the study will be terminated.

An Independent Safety Monitor with expertise consonant with the nature of risks involved with the study will oversee the study safety. Specifically, he will review the safety of the data after the first subject completed the study. He will be responsible for this review and decide whether the research should be altered or stopped. After this initial review, the Independent Safety Monitor will continue to monitor the study along with the investigator each time any adverse event or serious adverse event occurs regardless of whether such an event is study related or not.

The independent research monitor shall have authority to stop a research protocol in progress, remove individual human subjects from a research protocol, and take whatever steps are necessary to protect the safety and well-being of human subjects until the IRB can assess the monitor's report. The independent research monitor shall have the responsibility to promptly report their observations and findings to the IRB.

However, if any adverse effect occurs, the principal investigator will send, as immediately as possible, a report to the IRB for analysis. At least one physician investigator will be present throughout the entire study. Adverse events will be discussed with all research staff. All adverse effects associated with the use of the radioactive drug must will be reported directly to the RDRC and FDA.

X. REFERENCES

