The tools for diagnosis of VTE have evolved from contrast venography, ventilation-perfusion (V-Q) scans and pulmonary angiograms to D-dimer testing, venous duplex ultrasound and CT-angiograms. While these newer modalities are less invasive and more available; none is perfectly accurate and must rely on indirect measurements of clot, whether that is non-compressibility with ultrasound or filling defects with CT angiograms. Because of these limitations, it is recommended to improve the performance of the test through the use of Bayes' theorem, which incorporates pre-test probability to enrich the population for those that might or might not have VTE.⁷ Despite the high value of this recommendation when there is concordance between the pre-test probability and the test result, problems arise when there is discordance. For CT-angiograms, if the pre-test probability of PE is high, the negative predictive value is 60%.⁸ Conversely, if the pre-test probability of PE is low, the positive predictive value is 58%.⁸ In contrast, if pre- and post-test results are concordant, the positive and negative predictive value is 96%.⁸ The discordant situations lead to both under- and overdiagnosis if pulmonary artery angiogram is not pursued, and represent an area where targeted diagnostics utilizing a highly specific probe for newly cross-linked fibrin could help.

There are many other groups of patients at high risk for VTE that need targeted diagnostics. Venous thromboembolism is a disease of older age, with VTE virtually non-existent in adolescence but increasing in incidence rapidly with older age. Diagnosis becomes more difficult in older patients because of the diminished discriminatory power of D-dimer,^{9,10} the high prevalence of renal dysfunction that increases the risk of contrast dye nephropathy and precludes the use of contrast-enhanced CT angiography, and/or the high prevalence of lung disease that renders interpretation of V-Q scans difficult or impossible. Patients with prior DVT or PE present another diagnostic challenge. When the imaging method relies on filling defects to diagnose VTE, it is nearly impossible to distinguish old versus new clot. Here again is an area where targeted diagnostics utilizing a highly specific PET probe for newly cross-linked fibrin could help distinguish old clot from new, throughout the body.

[figure not shown]

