Our long-term research objective of this translational study is to establish a novel thrombus body scan (TBS) using a new fibrin-specific probe for positron emission tomography (PET) imaging to overcome the limitations of indirect VTE diagnosis, and, with one single test, provide a total-body assessment of fresh intravascular clot.

Scheme 1. Simplified synthetic route and chemical structure of ^{64}Cu -FBP8. The sequence of the core fibrin-binding peptide is reported on the bottom.

II. SPECIFIC AIMS

This proposal aims to generate strong evidence for VTE diagnosis using the thrombus body scan (TBS) from an initial small translational study that will justify a larger clinical study to obtain clinical approval for the TBS. We hypothesize that TBS using our new PET fibrin probe that specifically binds to fresh polymerized fibrin clot (< 1 week old), can directly detect thrombus anywhere in the body similar to ^{18}F -FDG PET scans for cancer nodules, will have better diagnostic accuracy for deep venous thrombosis and pulmonary embolus (DVT-PE) compared to current imaging modalities, can quantify the total body burden of fresh clot and can be performed in patients with renal dysfunction. Before we can fully test this hypothesis in an appropriately-powered clinical study, we propose a proof-of-concept study in a smaller cohort of patients to test the following specific aims and hypotheses:

1. Compare the presence, location and extent of PE diagnosed with the PET ⁶⁴Cu-FBP8 probe to conventional imaging. *Hypothesis:* The PET fibrin probe will allow direct imaging of acute thrombi causing PE, which is currently only indirectly diagnosed by filling defects on CT-angiogram or mismatched perfusion defects on V-Q scans.

2. Compare the presence, location and extent of DVT diagnosed with the PET ⁶⁴Cu-FBP8 probe to conventional imaging. *Hypothesis:* The PET fibrin probe will allow direct imaging of acute thrombi causing DVT diagnosed indirectly by incompressibility and loss of flow on lower extremity venous Doppler ultrasound.

3. In addition to PE and lower extremity DVT, assess for upper extremity and pelvic clot and compare the extent of total body clot burden imaged with the ⁶⁴Cu-FBP8 probe to the plasma D-dimer level. *Hypothesis:* The PET fibrin probe will discover acute thrombi including areas not assessed by current imaging methods and the total clot burden will correlate with the plasma D-dimer.

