Successful execution of this study will lay the groundwork for a clinical trial to compare the efficacy of a clot-specific imaging modality (**thrombus body scan or TBS**) that has the potential to be more accurate for the diagnosis of VTE, better able to establish the total clot burden in the body with a single test and more widely applicable to patients with renal failure and lung disease.

III. SUBJECT SELECTION

A total of eighty (80) subjects will be recruited for this study, which will be performed at the Massachusetts General Hospital (MGH). All eighty (80) subjects will be studied with the same protocol: a single injection of ⁶⁴Cu-FBP8 and PET-CT imaging at least three hours after injection at four bed positions, which will provide the imaging data for fresh blood clot at the three locations covering all three specific aims.

Inclusion Criteria:

Each subject must meet the following criteria to be enrolled in the study:

- 18 years of age or older with a clinically significant pulmonary embolus (PE) confirmed by a filling defect in CT angiography (CTA), and
- Subjects must receive the radiotracer injection within 72 hours of their diagnosis.

Exclusion Criteria:

- Subjects < 18 years of age
- Time of expected radiotracer injection > 72 hours from the time of a positive venous duplex ultrasound or CT-angiogram,
- Women subjects of childbearing potential who are pregnant, seeking to become pregnant, or have a positive serum pregnancy (beta-HCG) test,
- Unable to lie flat for 45 minutes as assessed by physical examination and medical history (e.g. back pain, arthritis, dyspnea),
- Weight that exceeds the PET camera table limit (300 kg)
- The subject will not be enrolled in the study if the radiation exposure for research studies during the prior 12 months, combined with the exposure from this study would exceed 50 mSv.
- Due to the radiation exposure from imaging studies, all women of childbearing potential will be required to have a negative serum pregnancy test performed prior to any imaging procedures on the same day (if not already done that day). Patients with a positive serum pregnancy test will be excluded. Breast feeding women will also be excluded.
- A pre-existing condition or use of a medication including vasopressors and tPA (due to its effects on clot) that in the opinion of the investigator may place the subject at a substantially increased risk
- Hemodynamic instability, including requiring escalating doses of vasopressor medication.

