- No groups designated as “special vulnerable populations” will be studied.
- No exclusions will be made based on race, sex, or ethnic origin.
- ⁶⁴Cu-FBP8 (Copper-64 labeled fibrin binding probe 8) is cleared by the kidneys, patients with eGFR < 30 will be excluded.

IV. SUBJECT ENROLLMENT

Identification of eligible subjects will be done from 1) admissions to the Massachusetts General Hospital for treatment of pulmonary embolus (PE) 2) admissions to MGH for other indications but with an acute PE at admission or during hospitalization, 3) patients who present to the Emergency Department with an acute PE, but will not be admitted to the hospital. The subjects will be identified through the MGH Pulmonary Embolus Response Team (PERT), radiology notifications or running PeRC Epic team report, which could identify inpatients who were not picked by PERT or radiology notifications, or through patients physician investigators may be aware of that have an acute PE. PERT is a well-established group of cardiologists, pulmonologists, interventional radiologists, emergency room physicians, and cardiac surgeons who are “on-call” when a clinician anywhere in the hospital suspects a patient has a clinically significant pulmonary embolus. When PERT is activated, a fellow organizes a web-based meeting within minutes through a page and email to the participating physicians. The data is reviewed via “go-to-meeting” conference and a treatment plan is decided upon by consensus. An email will be sent to [name], and [name] when PERT is activated and [name] will assess whether the patient is appropriate and potentially eligible for the study. Also, since the fibrin probe must be manufactured at MGH Navy Yard and sent to MGH main campus, only patients diagnosed at a time when they can receive the radiotracer within 72 hours of their diagnosis will be included. If the patient meets eligibility criteria, the patient’s treating physician will be contacted to ask the patient for permission to be contacted by the study staff. During the first contact, the physician co-investigator will screen the subject for eligibility and describe the study and its implications, risks and benefits. If the subject is interested, the consent form will be given to the subject to read. The subject will be given as much time as necessary to decide, however if a decision cannot be made within the 72-hour limit from initial diagnostic imaging to the fibrin probe injection, or not before a scheduling time window for fibrin injection, the subject will be excluded. We will allow as much time as necessary for the subject’s questions to be answered or for the subject to consult family members or treating doctors before the consent form is signed. After the subject signs the consent form, the original signed consent form will be kept on file, a copy will be given to the subject, and a copy will be scanned to the subject EMR. No study procedures will be performed prior to the subject signing the informed consent document. The informed consent process will be accurately documented in the subject medical records.

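### Clot age is neither recorded nor analysed, so clot seen on CTA but not on PET cannot be read as probe failure or as correctly unlabelled old clot

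*Combined protocol and SAP*

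**What the plan says.** All references are to the combined protocol and SAP.

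- **Target (Section II).** The overall hypothesis is that the probe "specifically binds to fresh polymerized fibrin clot (< 1 week old". The Aim 1 hypothesis is narrower: "The PET fibrin probe will allow direct imaging of acute thrombi causing PE". Aims 2 and 3 also speak of acute thrombi.
- **Entry (Section III).** The qualifying finding is a "clinically significant pulmonary embolus (PE) confirmed by a filling defect in CT angiography (CTA". The clock is "Subjects must receive the radiotracer injection within 72 hours of their diagnosis", and the matching exclusion is "Time of expected radiotracer injection > 72 hours from the time of a positive venous duplex ultrasound or CT-angiogram". No criterion limits symptom onset or excludes prior VTE.
- **Recruitment (Section IV).** One route is "admissions to MGH for other indications but with an acute PE at admission or during hospitalization". The emergency department route and the investigator-identified patients are also described as acute. The route for patients admitted for PE treatment is not, and no definition is given.
- **Dating clot (Section I).** In discussing patients with earlier DVT or PE, the protocol says: "When the imaging method relies on filling defects to diagnose VTE, it is nearly impossible to distinguish old versus new clot".
- **Data (Section V).** A physician takes a detailed history, and history findings count as research material. The list of variables for the database includes neither onset date nor prior VTE.
- **Analysis (Section VI).** Blinded readers call clot present or absent at each site. Aim 1 compares PET regions with CTA filling defects, and Aim 2 compares them with duplex. The one overlap fraction defined for Aim 1 divides the intersection by the PET thrombus volume. No comparison uses clot age or a proxy for it.

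**The concern.** The hypothesis is limited by clot age, while entry is limited by time since the scan. These are different clocks, and nothing in the plan links them. A subject with two or three weeks of symptoms, or with residual old clot beside new clot, can meet the listed criteria if the PE is clinically significant and the CTA is recent.

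Because every subject is CTA-positive, the informative discordance in Aim 1 is a filling defect without PET uptake. It has two opposite meanings: the probe failed on fresh clot, or it behaved as hypothesised and did not label old clot. Separating old from new clot is one of the stated reasons for developing the probe. The study is also meant to justify a larger one, so an ambiguous level of agreement would carry into that study's design.

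**Working it through.** The plan gives no expected sensitivity, power or target agreement, so there is no figure of its own to reproduce. Three checks follow.

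**1. The two clocks.** The hypothesis limit is 7 × 24 = 168 h (Section II). The latest permitted injection is 72 h after diagnosis (Section III). For a subject injected at that limit, clot is under 1 week old only if it formed less than 168 − 72 = 96 h before the CTA. No criterion or data field checks this.

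**2. What the defined overlap fraction can show.** Take a CTA defect volume of 10 units and suppose PET labels all the fresh part and none of the old part.

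| Fresh | Old | Intersection / PET volume | Intersection / CTA volume |
|---|---|---|---|
| 10 | 0 | 10/10 = 1.0 | 10/10 = 1.0 |
| 7 | 3 | 7/7 = 1.0 | 7/10 = 0.7 |
| 4 | 6 | 4/4 = 1.0 | 4/10 = 0.4 |

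The planned fraction stays at 1.0 however much CTA clot PET leaves unlabelled. With no PET region it is 0/0, whereas the CTA-denominator fraction is 0. PET-negative clot therefore does not lower the planned measure. It shows only in the comparison of presence and extent.

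**3. Why the presence comparison cannot separate the two causes.** This is an illustration, and its inputs are assumptions. Let Se be detection in subjects with fresh clot, and q the share of subjects whose CTA clot is all over 1 week old and PET-negative. If subject-level agreement with CTA were tabulated in 80 subjects, its expected value would be Se × (1 − q):

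- Se = 0.90, q = 0: 0.90, or 72/80
- Se = 0.95, q = 5%: 0.9025, or about 72/80
- Se = 1.00, q = 10%: 0.90, or 72/80

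All three give 72/80 (exact 95% CI 81.2% to 95.6%). Without information on q, the result does not identify Se.

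With Se held at 0.95, the range is:

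| q | Se × (1 − q) | Rounded count | Exact 95% CI |
|---|---|---|---|
| 0 | 0.95 | 76/80 | 87.7% to 98.6% |
| 5% | 0.9025 | 72/80 | 81.2% to 95.6% |
| 10% | 0.855 | 68/80 | 75.3% to 92.0% |
| 20% | 0.76 | 61/80 | 65.4% to 85.1% |

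A subject with both old and new clot would still be PET-positive if the new clot binds the probe. Such subjects affect extent, not presence.

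**The case against.** There is a fair case that the gap is small.

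- **No scoring rule.** A reader might infer that PET-negative old clot is scored as a miss. The documents do not say so. They define no sensitivity, do not name CTA as truth and give no rule for discordance, and the one overlap fraction is unaffected by PET-negative clot. This stands. What remains is that such clot appears as unexplained disagreement in presence and extent, which Aims 1 and 2 set out to compare.
- **Deferred hypothesis.** A reader might infer that the study cannot test its own hypothesis. Section II leaves full testing of the overall hypothesis to a later, powered study, and whether acute thrombi can be imaged directly can be examined in this cohort without an age contrast. This stands too. The ambiguity concerns how negative findings are read.
- **Scope of the dating remark.** Section I says nearly impossible, not impossible, and the remark concerns patients with prior VTE and filling-defect imaging. It should not be stretched to every filling defect or to duplex. But patients with prior VTE may enrol.
- **Recruitment wording.** Most routes refer to acute PE, and the PE must be clinically significant. This reduces the share of old clot but, with acute undefined, does not remove it.
- **Weak proxy.** Symptom onset does not date clot formation, and an incidental inpatient PE may have no onset date. True, but the plan now has no proxy at all.

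**Conclusion.** The point holds as a problem of interpretation. The target is defined by clot age, entry by time from the scan, and no clot-age information is specified for recording or analysis. CTA-positive, PET-negative clot therefore cannot be divided into probe failure and correctly unlabelled old clot. The same gap affects Aim 2, where duplex clot is compared without regard to age.

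The 96 h figure follows from the protocol's own limits. The size of the effect is unknown, because the documents do not give the share of older clot or the probe's detection rate in it. The agreement figures above rest on assumed inputs, for a summary that the plan does not name, and only show how the two explanations merge. The documents do not support concluding that the study is invalid or that old clot is counted against the probe by rule. The change is worth making because it is cheap and because onset dates become harder to recover once enrolment ends.

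**What to change.** Leave eligibility unchanged.

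1. Add two database fields, filled from the history already taken: symptom-onset date (allowing unknown or incidental) and prior VTE.
2. Compute time from onset to injection.
3. Pre-specify PET detection, TBR and overlap for onset up to 7 days, onset over 7 days, and unknown onset or prior VTE, plus a trend over continuous onset-to-injection time. Report all subjects alongside.
4. Keep the planned overlap fraction and add one with the CTA filling-defect volume as denominator, so that PET-negative clot is visible and subjects with no PET region have a defined value.

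The cost is two data fields, one stratified summary with a trend, and one further ratio from regions already drawn. Onset is an imprecise proxy for clot age, and each group will be smaller than 80, so these results should be labelled descriptive.

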Patients will be contacted at 3, 6 and 12 months following the diagnosis of PE. Death and recurrence of DVT-PE will be assessed. Results of any imaging studies (CT angiograms, echocardiograms, or venous duplex ultrasound studies) and serologic studies (follow up d-dimer) will be collected and patients will undergo a survey to collect information about symptoms attributable to PE-DVT as well as quality of life using Standard Form 36,²⁸ VEINES QOL29 and the patient's self-assessment of their overall health status on a 1 – 10 scale, with 1 indicating the worst possible and 10 the best possible health. For patients followed at MGH this will be done in person at the end of their PERT or pulmonary clinic follow up clinic visit. For those followed elsewhere, this will be done by telephone with subjects and their treating physicians. NYHA functional class, 6-min walk distance, and change in pulse oximetry with walking will be assessed.

VI. BIOSTATISTICAL ANALYSIS

Once a patient is enrolled, the subjects will receive an injection of up to 10 mCi ⁶⁴Cu-FBP8 and imaged with CT-PET approximately at least 3 hours after injection, when the “target-to-background” ratio (TBR) of activity is expected to be high based on previous studies.²⁷ With CT-PET the attenuation correction is done using a low-dose CT volumetric scan. Afterwards, PET acquisitions of 10 min duration each are performed in four positions, thorax, pelvis and thighs (2 positions), which are used to assess regional ⁶⁴Cu-FBP8 activity.

Specific data variables:

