The standardized uptake value (SUV) of ⁶⁴Cu-FBP8 uptake in the lungs, pelvis and thighs will be calculated. The target to background ratio (TBR) for ⁶⁴Cu-FBP8 activity will be calculated using as background a region of interest (ROI) created from large cardiac and vascular structures. This corrects the ⁶⁴Cu-FBP8 activity for differences in injected dose and timing of imaging and allows for flexibility in the image timing. One member of our group ([name]) and another from Nuclear Medicine ([name]) will be blinded to the clinical results and will identify the presence or absence of clot in the three imaged locations as well as the anatomic location(s) and extent as best as possible from the overlay of the fibrin activity on the attenuation correction CT scans. Additionally, we will perform quantitative image analyses including the volume of the thrombus ROI, activity of imaged clot in each imaged section and clot burden. The thrombus ROI is defined by a threshold of 50% between peak activity of the ROI and background activity. Multiple ROIs will be used in the case of separated thrombi. Clot burden will be estimated using the sum of ⁶⁴Cu-FBP8 activity within a thrombus ROI and then normalized by the injected dose.

Outcome Measures:

Specific Aim 1: The location and extent of the thrombus region of interest (ROI), its volume and clot burden within the lung ROI will be compared with the ROI of filling defects on CT-angiogram. We will determine the number and location of the thrombus ROI(s) within the lungs, and the overall clot burden as sum of ^{64}Cu -FBP8 activity within a thrombus ROI(s) within the lungs. Additionally, we will calculate the intersection of the thrombus ROI and filling defects ROI relative to volume of the thrombus ROI. That will quantify the fraction of thrombus ROI(s) using a scale from being are completely outside (0) to completely inside (1). Also, we will perform a lung segmentation using the software APOLLO (VIDA Diagnostics) and determine in which lung lobe the thrombus ROI(s) are located.

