Specific Aim 2: The thrombus ROI, its volume and clot burden within the thigh ROI will be compared with the location and extent of the clot on venous duplex ultrasound. We will determine the number and location of the thrombus ROI(s) within the thigh ROI, and the overall clot burden as sum of ^{64}Cu -FBP8 activity within a thrombus ROI(s) within the thigh ROI. Additionally, we will quantify the volumes and locations of the thrombus ROIs of the PET scan and the venous duplex ultrasound relative to each other. Also, we will perform a vessel segmentation using the 3D Slicer (open source software) and determine the location of thrombus ROI(s) with the blood vessel.

Specific Aim 3: The prevalence of high ^{64}Cu -FBP8 fibrin activity in the pelvic ROI and upper extremity ROI's will be reported. Additionally, as a secondary analysis, both the total fibrin activity in the imaged fields, excluding the liver, gallbladder, kidneys and urinary bladder normalized by injected dose for all patients will be correlated with the plasma D-dimer drawn at the time of imaging. D-dimer levels will be drawn daily from the time of first diagnostic imaging to the fibrin probe imaging (up to 3 days maximum in total) as well as PT, PTT, platelets and fibrinogen. Anticoagulants used, as well as timing and dose will be carefully recorded during this period.

For all Specific Aims, death, VTE recurrence, and quality of life measures will be compared with the clot burden measured by PET and conventional imaging modalities, stratified by treatment (systemic thrombolysis, catheter thrombolysis, or heparin alone) using multiple correlation, ANOVA, and t-tests for pairwise comparisons.

VII. RISKS AND DISCOMFORTS

^{64}Cu -FBP8 PET probe:

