for identification of incidental findings. If incidental findings are identified and the subject gives consent, we will provide this information to the subject's primary care physician. If clot is identified by the fibrin scan in places not seen or not evaluated by the treating team (e.g. the pelvis), this information will be conveyed to the treating team and appropriate clinically-approved testing can be done to assess this if the treating team deems it necessary.

Venous thromboembolism (VTE), comprising deep venous thrombosis and pulmonary embolism, is a major public health problem. The estimated average annual incidence rate of overall VTE among persons of European ancestry ranges from 104 to 183 per 100,000 person-years and is similar to that of stroke,¹ the fifth leading cause of death in 2013.² Incidence rates for PE±DVT are 29 to 78 per 100,000 person-years and for leg DVT alone are 45 to 117 per 100,000 person-years.¹ For those of African descent, the incidence may be higher.³⁻⁵ Over the decade from 2002 to 2012, the incidence of VTE has been rising.⁶ This has raised the question of whether this rise represents a true increase in incidence or potentially over diagnosis with more available imaging techniques. Whatever the reason, it is clear from this data that it is vitally important to improve the accuracy of identifying VTE with targeted diagnostics. The knowledge gained from this study will allow an assessment of whether or not a fibrin-specific PET probe has the potential to improve our diagnostic accuracy of VTE, diagnose VTE in previously difficult areas (pelvis) and broaden the patient population on which specific diagnostic testing can be performed, such as those with renal failure.

IX. MONITORING AND QUALITY ASSURANCE

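### Aim 3's prevalence of high pelvic and upper-extremity uptake has no reference, positivity rule or verification status, so alone it cannot support the hypothesis that PET discovers acute thrombi

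*Combined protocol and SAP*

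**What the plan says.** Section II, Aim 3, sets out to assess upper-extremity and pelvic clot. Its hypothesis is that the probe will "discover acute thrombi including areas not assessed by current imaging methods", and that total clot burden will correlate with D-dimer.

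Section VI gives the measurement. Two readers blinded to the clinical results "will identify the presence or absence of clot in the three imaged locations", working from PET overlaid on the attenuation-correction CT. The preceding text names the locations as lungs, pelvis and thighs. On extent, "The thrombus ROI is defined by a threshold of 50% between peak activity of the ROI and background activity".

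The Aim 3 outcome in Section VI for the otherwise unimaged regions is one sentence: "The prevalence of high" probe uptake, that is "fibrin activity in the pelvic ROI and upper extremity ROI's will be reported". A secondary analysis correlates total activity with D-dimer, and there the liver, gallbladder, kidneys and urinary bladder are excluded.

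The other two aims have comparators. In Aim 1 the PET findings "will be compared with the ROI of filling defects on CT-angiogram"; in Aim 2 they are compared with venous duplex ultrasound.

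Two other places bear on verification. Section VIII says that clot seen only on the fibrin scan, with the pelvis as example, is reported to the treating team, and that "appropriate clinically-approved testing can be done to assess this if the treating team deems it necessary". Section V, Follow up, collects "Results of any imaging studies (CT angiograms, echocardiograms, or venous duplex ultrasound studies") at the 3, 6 and 12 month contacts, and the Study Events table schedules a record review at the same times. Nothing links these results to the PET finding.

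**The concern.** The hypothesis and the reader task speak of thrombus, while the outcome counts high activity. The step from one to the other is not tested anywhere in the plan. In the lungs and thighs a PET call can be set against another modality. In the pelvis and upper extremities it cannot, so a true clot and a false positive add equally to the reported figure.

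The protocol's own facts make false positives possible, though they do not show that they occur:

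- The probe is cleared by the kidneys (Section III), and Section VII lists the urinary bladder among the organs with the highest dose. The bladder exclusion is written for the total-activity analysis only.
- Section I ties fibrin deposition to cancer and inflammation as well as to thrombosis.
- The 50% rule is relative to each region's own peak. It draws the outline of a focus and does not decide whether the focus is positive.
- All subjects have PE confirmed by CT angiography, so no VTE-free group exists from which to estimate a false-positive rate.

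At stake is what the trial may conclude. Section VIII expects the study to inform whether the probe can diagnose VTE in the pelvis, and Section II wants evidence strong enough to justify a larger study.

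**Working it through.** **The plan's own figures.** The only relevant number is the sample size, 80 (Section III). The documents give no expected prevalence, sensitivity, specificity or precision target, so there is no calculation to reproduce. What follows is illustration on assumed inputs.

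**Inputs.** n = 80, from Section III. Assumed: sensitivity Se = 0.90; specificity Sp = 0.90, 0.95 or 0.98; true prevalence of pelvic clot π = 0, 5%, 10% or 20%. The unit is the subject.

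**Formulas.** True positives TP = 80 × π × Se. False positives FP = 80 × (1 − π) × (1 − Sp). Apparent prevalence = (TP + FP)/80. Positive predictive value PPV = TP/(TP + FP).

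Worked example, π = 5% and Sp = 0.95: TP = 80 × 0.05 × 0.90 = 3.6; FP = 80 × 0.95 × 0.05 = 3.8; apparent prevalence = 7.4/80 = 9.3%; PPV = 3.6/7.4 = 49%.

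| π | Sp | TP | FP | Apparent prevalence | PPV |
|---|---|---|---|---|---|
| 5% | 0.90 | 3.6 | 7.6 | 14.0% | 32% |
| 5% | 0.95 | 3.6 | 3.8 | 9.3% | 49% |
| 5% | 0.98 | 3.6 | 1.5 | 6.4% | 70% |
| 10% | 0.90 | 7.2 | 7.2 | 18.0% | 50% |
| 10% | 0.95 | 7.2 | 3.6 | 13.5% | 67% |
| 10% | 0.98 | 7.2 | 1.4 | 10.8% | 83% |
| 20% | 0.90 | 14.4 | 6.4 | 26.0% | 69% |
| 20% | 0.95 | 14.4 | 3.2 | 22.0% | 82% |
| 20% | 0.98 | 14.4 | 1.3 | 19.6% | 92% |

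**No pelvic clot at all (π = 0).** Expected false positives are 80 × (1 − Sp): 8 at Sp 0.90, 4 at 0.95 and 1.6 at 0.98. The chance of at least one is 1 − Sp^80: more than 99.9%, 98% and 80%. So a non-zero prevalence is likely even when the hypothesis is false for the pelvis. With perfect specificity the problem vanishes, but the plan has no means of showing that.

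**What verification status would add.** Suppose 8 of 80 subjects are PET-positive in the pelvis, with one finding each, 4 are tested and 2 are confirmed (all assumed). Intervals are exact (Clopper-Pearson) 95%.

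- Every positive counted as clot: 8/80 = 10.0% (4.4% to 18.8%).
- Untested counted as negative: 2/80 = 2.5% (0.3% to 8.7%).
- Untested counted as positive: (2 + 4)/80 = 6/80 = 7.5% (2.8% to 15.6%).

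The bounds concern PET-positive subjects only. Clot that PET misses remains unknown.

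**The case against.** The outcome is worded as activity, not clot, and no test or success rule turns the prevalence into a claim of discovery. That is correct. The gap opens only when the figure is used for the hypothesis, which is the use Sections II and VIII point to.

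Safeguards exist. Two blinded readers call clot with anatomic location on the CT overlay, so raw pelvic uptake is not automatically thrombus. The bladder is excluded from total activity, and subjects void before the scan, though the stated purpose is to limit movement. These stand, and the fix builds on them. They do not supply a reference.

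The size rests wholly on assumptions. In subjects who all have PE, 5% to 10% may be too low, and at 20% the PPV is 69% or better. This stands too. A reader might infer from the low-prevalence rows that most pelvic findings will be false. The documents do not support that; they leave the proportion unknown.

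A reader might also infer that the confirmatory data are already in hand. They are not. Testing is at the treating team's discretion, the imaging listed under Follow up names no pelvic venous study and none is mandated, and a scan months later on treatment cannot reliably refute a clot seen at baseline.

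Finally, the confirmed share among tested findings will be imprecise: 2 of 4 has an exact 95% interval of 7% to 93%. It is also selected, and conventional imaging is itself imperfect, as Section I says. That argues for showing bounds over all subjects, not for leaving verification out.

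**Conclusion.** The concern holds in a limited form. As written, the prevalence of high activity in the pelvis and upper extremities cannot on its own support the hypothesis that PET discovers acute thrombi there, because false positives count toward it and the analysis does not separate them. This follows from the text and needs no assumed figure.

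The size is not known. Under sensitivity 90% and specificity 90% to 98%, PPV runs from 32–70% at 5% true prevalence to 69–92% at 20%. These figures show how far the answer depends on quantities the plan does not estimate; they do not predict the result.

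It would go too far to say that the trial cannot answer Aim 3. The D-dimer correlation is untouched, and the prevalence of PET-positive uptake is a legitimate descriptive result for a proof-of-concept study. The limit applies to the discovery claim. The change is worth making because it is cheap and sets what the trial may conclude.

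**What to change.** Amend the Aim 3 outcome in Section VI as follows.

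1. Report the number of subjects with PET-positive focal intravascular uptake in each region, as called by the two blinded readers already planned. State the positivity rule, have the readers call the upper-extremity regions as well as the three locations now named, and apply to the pelvis the urinary-activity exclusion already used for total activity.
2. Tabulate each PET-positive finding as confirmed, refuted or untested. Use clinical testing prompted by the PET report (Section VIII) and imaging retrieved at record review and follow-up (Section V). Accept only imaging done within a prespecified short window of the PET scan.
3. Give the confirmed share of all subjects as bounds, with untested findings counted first as negative and then as positive, each with an exact 95% confidence interval. State that the tested findings are a clinician-selected subset.
4. Limit any claim of discovered thrombi to confirmed findings, and call the rest unverified PET-positive uptake.

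The cost is analysis wording and linking existing records to PET findings; no new scans or readers are needed. The downside is a small, selected confirmed number and a less favourable headline. Only partial verification data can be expected. Systematic confirmation would need imaging that the protocol does not provide.
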